5.4 Replacement policy

There will be no replacement of patients who have been withdrawn or who dropped out after randomization.

6 DESCRIPTION OF TREATMENTS

Subject will be randomly allocated to receive either:

- AEZS-108 - Investigational drug (Arm A)
- OR
- Doxorubicin – Comparator drug (Arm B).

Details related to AEZS-108 (Arm A) are presented in [Section 6.1](#) while those related to doxorubicin (Arm B) are provided in [Section 6.2](#). Information provided in [Section 6.3](#) to [Section 6.4](#) is applicable to both, Arm A and Arm B.

6.1 Investigational drug – AEZS-108

6.1.1 Description / general issues

Description: AEZS-108 is formulated as a powder (lyophilisate) and provided in glass vials containing 100 mg of the active substance, without additional excipients. The 100 mg vials are further packaged in boxes. Vials and boxes will be labeled as shown in a copy in the investigator's file.

Retest date, manufacturing date: Trial medication may not be used after a retest date specified on a drug product label. Replacement of such medication with new or relabeled medication, indicating the revised retest date, is required.

Where allowed by local regulations, the label of the trial medication will specify the manufacturing date. Such medication may not be used after the retest date, which is specified in the certificate of analysis.

Responsibility at the study center: The investigator is responsible for the appropriate storage and distribution of the investigational products and will observe the applicable regulations. The investigator may name a responsible person, e.g. pharmacist, to take care of the trial medication.

Supply: Trial medication will be shipped to a responsible person at the investigator's institution who will check amount and condition of the drug received and will return an acknowledgement of receipt to Aeterna Zentaris.

Storage: The trial medication can be stored in a refrigerator, at temperatures between 2 and 8 °C, protected from light. The trial medication may not be used after the specified retest/expiry date.

Accountability: The responsible person at the study center has to account for all used and unused trial supplies of AEZS-108 and has to complete a *Medication Accountability List* that includes the following information:

- identification of patient (number and initials),
- date and quantity of drug dispensed,
- date and quantity of drug returned to Aeterna Zentaris.

At the end of the trial, or as directed, residual supplies and the completed *Medication Accountability List* will be returned to Aeterna Zentaris, a copy of the completed list will be retained in the Investigator's file.

The trial medication must not be used outside this protocol.

6.1.2 Reconstitution and administration

Reconstitution and dilution: Physiological saline (0.9 % NaCl solution) will be used as solvent for the reconstitution and dilution of AEZS-108 solution.

Four (4) mL of saline will be added per 100 mg vial, resulting in a concentration of 25 mg AEZS-108 per mL of the reconstituted solution.

The appropriate volume of reconstituted AEZS-108 solution will be diluted with physiological saline, such as to contain the desired amount of drug substance in an infusion volume of about 250 mL.

Stability in diluted solution: Not more than 1 hour should elapse between dissolution of the lyophilisate and the preparation of the solution for infusion. The diluted solution for infusion can be stored at room temperature, but must be completely infused within 7 hours after dissolution of the lyophilisate.

Administration (Infusion): The administration schedule is as follows:

Dose:	267 mg/m ² ; For each treatment course, dose calculation will take into account the body surface area (BSA) as derived from the patient's height and current body weight. (Note: If the body weight is +/- 10% of the body weight measured at day 1 of the preceding cycle, the body weight measured at day 1 of the preceding cycle may be used for calculating the dose to be prepared in the pharmacy). Appendix 1 provides a nomogram and reference to online BSA calculators for the determination of the BSA.
Route:	Intravenous infusion over a period of about 2 hours
Frequency:	Every Day 1 of 21-day (3-week) cycles
Duration:	The proposed maximum duration is 9 cycles. An individual patient will be withdrawn from study as soon as disease progression indicates treatment failure or poor tolerability requires withdrawal. (see Section 5.3 for withdrawal criteria).
Premedication	Recommended prophylactic antiemetic: 8 mg dexamethasone (see Section 6.3)
Warning:	Paravenous administration must be avoided: In rabbits, paravenous injection resulted in inflammatory reaction and necrosis of muscle cells. Extravasation may occur with or without an accompanying stinging or burning sensation, even if blood returns well on aspiration of the infusion needle. If any signs or symptoms of extravasation have occurred, the infusion should be immediately terminated and restarted in another vein. In the case of extravasation during infusion, it should be treated according the guidelines for therapy of doxorubicin extravasates. In addition to general treatment procedures for cytostatic extravasates, dimethyl sulphoxide (DMSO) 99 % should be applied to the entire extravasation area every 3 - 4 hours for at least 14 days.

6.1.3 Treatment modifications / delay of treatment

Any deviation from the planned dosing schedule must be commented on in the CRFs.

Delay of re-treatment: Subsequent cycles of study treatment should not begin before a patient has recovered to CTCAE Grade 1 from a drug-related adverse event (i.e., causality at least possibly related) that the investigator feels is clinically significant. No treatment delay is required for alopecia or anemia for which supportive therapy should be given according to study sites' clinical practice (see also 6.3.1.3). Re-treatment may be postponed for up to 2 weeks. A patient who has not recovered within 5 weeks after the last dose should be withdrawn and followed up as required.

Dose reduction: Any of the following drug-related adverse events (i.e., causality at least possibly related) will require a dose modification, if its duration exceeds the indicated period:

- Grade 4 neutropenia [ANC < 500/mm³] lasting 7 days or more

- Grade 3 febrile neutropenia lasting for more than 7 days
[Grade 3 defined as: ANC < 1000/mm³ with a single temperature of >38.3 °C (101 °F) or a sustained temperature of ≥ 38 °C (100.4 °F) for more than one hour]
- Grade 4 febrile neutropenia (of any duration)
[Grade 4 defined as: Life-threatening consequences; urgent intervention indicated]
- Grade 3 thrombocytopenia [Platelet count: < 50,000 – 25,000/mm³] persistent at the scheduled time of re-dosing (i.e. blood sample on the day before re-dosing) and associated with a clinical risk of bleeding (presenting, e.g. as hemorrhagic diathesis: petechial rash, especially affecting tunica mucosa in oral cavity, gingival rash or petechial skin rash associated with prolonged bleeding time, e.g. in the Duke bleeding time test)
- Any other Grade 4 hematological toxicity (except for lymphocytopenia) lasting 7 days or more
- Grade 3 nausea/vomiting/diarrhea lasting 5 days or more despite optimal medical management.

If any of the above dose-limiting toxicities occurs and re-treatment is indicated after the toxicity has resolved to ≤ Grade 1 within the allowed period for a treatment delay, then dosing will be resumed with a dose reduction.

Dose Level	AEZS-108 Dose (mg/m ²)
Starting Dose	267
1 st Dose Reduction (approximate 20 % reduction)	210
2 nd Dose Reduction (approximate 40 % reduction)	160

The dose reduction is permanent; no dose re-escalation to the original dose should be permitted once a dose has been reduced. Only 2 dose reductions per patient will be allowed. Patients who cannot tolerate the lowest dose will be discontinued and may receive other treatments at the investigator's discretion.

Supportive therapy (see also [Section 6.3.1](#)): Hematopoietic growth factors or transfusion of blood components may be administered as needed, e.g. in case of a delayed hematological recovery or in case of hematological toxicities with a shorter duration than specified above for DLTs.

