19. Concomitant or recent treatment with other investigational drug (within 4 weeks or 5 elimination half-life times prior to anticipated start of study treatment).

Administrative reasons:

20. Lack of ability or willingness to give informed consent.
21. Anticipated non-availability for study visits/procedures.

Study medication, dose, and mode of administration

AEZS-108	INN zoletarelin doxorubicin, acetate salt
Presentation:	100 mg lyophilisate per vial
Dosage scheme:	267 mg/m ² by 2-hour intravenous infusion, on Day 1 of 21-day (3-week) cycles Note: If the body weight is +/- 10% of the body weight measured at day 1 of the preceding cycle, the body weight measured at day 1 of the preceding cycle may be used for calculating the dose to be prepared in the pharmacy
Maximum duration / dose:	The proposed maximum duration is 9 cycles.
Treatment delay:	up to 2 weeks in case of persisting clinically significant adverse reactions (except for alopecia); for details, see Protocol Section 6.3.1.3.
Dose reduction:	210 mg/m ² in case of dose-limiting toxicity or delayed recovery
Doxorubicin	doxorubicin HCl (non-liposomal formulation)
Presentation:	commercial product (trade name, e.g., Adriamycin)
Dosage scheme:	60 mg/m ² by intravenous bolus injection, 1-hour intravenous infusion, or according to standard institution procedures, on Day 1 of 21-day (3-week) cycles Note: If the body weight is +/- 10% of the body weight measured at day 1 of the preceding cycle, the body weight measured at day 1 of the preceding cycle may be used for calculating the dose to be prepared in the pharmacy
Dose adjustment:	(for starting dose)
- Renal function	at glomerular filtration rate (GFR) below 10 ml/min.: 75 % of calculated dose
- Hepatic function	at serum bilirubin 1.2 to 3.0 mg/100 mL: 50 % of calculated dose;

Maximum duration / dose:	at serum bilirubin > 3.0 mg/100 mL: 25 % of calculated dose up to a cumulative lifetime dose of 550 mg/m ²
Treatment delay:	up to 2 weeks in case of persisting clinically significant adverse reactions (except for alopecia); for details, see Protocol Section 6.3.2.3.
Dose reduction:	(for retreatment) 50 to 75 % of starting dose if required by dose-limiting toxicity or delayed recovery

Criteria for evaluation (efficacy, safety)

1. Overall survival (primary efficacy endpoint).

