8.4.3 Procedures on Day 1 of Cycle 2-9

It will be allowed to schedule tests up to 3 days before the planned Cycle Day 1, to ensure availability of safety-relevant results prior to dosing.

- **Interval history** and symptom-directed examination
Adverse changes to be recorded as Adverse Events
- **Clinical assessments** (including ECOG performance status, blood pressure, pulse, and weight for BSA and dose calculation). Note: If the body weight is +/- 10 % of the body weight measured at day 1 of the preceding cycle, the body weight measured at day 1 of the preceding cycle may be used for calculating the dose to be prepared in the pharmacy.
- **Clinical laboratory tests** (hematology, chemistries, urinalysis, hormones)

- **Cardiac function:**
 - 12-lead electrocardiogram (ECG)
- **Study treatment**

If dose-limiting toxicities have been observed in a previous cycle, the dose of the study treatment will be reduced in the next cycle (as well as in further cycles), as specified in [Section 6.1.3](#) or [6.2.3](#).
- **Sparse PK sampling (AEZS-108 treated patients only)**

A patient in whom sparse PK sampling was not possible in Cycle 1 may have the samples taken at any subsequent cycle. It is not planned to have repetitive sparse sampling of the same patient during multiple cycles.

Blood collections within the following time windows:

 - sample #1: within 60 minutes before end of the 2-hour infusion
 - sample #2: between 30 and 60 minutes after the end of infusion (EOI)
 - sample #3: between 120 and 180 minutes after EOI;
 - sample #4 (optional): between 4 and 6 hours after EOI.

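### Section 6.1.3 requires an AEZS-108 dose reduction after 5 days of Grade 3 vomiting or diarrhea, but not after a short Grade 4 episode that has resolved by re-dosing

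*Protocol*

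**What the plan says.** Protocol section 6.1.3 states that a listed event, if at least possibly drug-related, "will require a dose modification, if its duration exceeds the indicated period". There are six entries:

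- Grade 4 neutropenia for 7 days or more
- Grade 3 febrile neutropenia for more than 7 days
- Grade 4 febrile neutropenia at any duration
- Grade 3 thrombocytopenia still present at re-dosing with a clinical bleeding risk
- other hematological toxicity of Grade 4, lymphocytopenia excepted, for at least 7 days
- "Grade 3 nausea/vomiting/diarrhea lasting 5 days or more despite optimal medical management"

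The first reduction goes from 267 to 210 mg/m². The sentence on resuming treatment at a lower dose applies to the toxicities listed above it.

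Two other places mention dose reduction. The synopsis (study medication) reduces to 210 mg/m² "in case of dose-limiting toxicity or delayed recovery". Section 8.4.3 says "If dose-limiting toxicities have been observed in a previous cycle, the dose of the study treatment will be reduced" and refers to 6.1.3 (AEZS-108) or 6.2.3 (doxorubicin) for the details. SAP section 6.4 only summarizes the modifications that occurred.

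**The concern.** Five of the six entries are hematological. The gastrointestinal entry names Grade 3 alone, and the general Grade 4 entry stops at hematological toxicity. A Grade 4 gastrointestinal episode therefore triggers a reduction only if it also spends at least 5 days at Grade 3.

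This looks like an omission. The list has three Grade 3 entries, and two of them have a Grade 4 counterpart: febrile neutropenia has its own Grade 4 line, and thrombocytopenia is covered by the general hematological line. Only the gastrointestinal entry has none. For febrile neutropenia the list spells out what Grade 4 means, "Grade 4 defined as: Life-threatening consequences; urgent intervention indicated", and acts on it at any duration.

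What is at stake is patient safety on re-dosing, and a single rule across approximately 120 study locations in an open-label trial. A mandatory list sets a minimum. Here the minimum covers 5 days of Grade 3 but not a shorter episode that reached Grade 4.

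**Working it through.** **Text check.** Take drug-related Grade 4 vomiting or diarrhea with fewer than 5 days at Grade 3, recovered to Grade 1 by the scheduled re-dosing day.

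| Rule | Applies? |
|---|---|
| Five hematological entries in 6.1.3 | No, the event is not hematological |
| Gastrointestinal entry in 6.1.3 | No, fewer than 5 days at Grade 3 |
| Synopsis, delayed recovery | No, Grade 1 by re-dosing |
| Synopsis, dose-limiting toxicity | Not defined there; 6.1.3 uses the term for its own list |
| Section 8.4.3 | Refers back to 6.1.3 |
| Delay rule in 6.1.3 | Satisfied; it governs timing, not dose |
| Sections 5.3 and 6.1.2 | Allow withdrawal for poor tolerability; require no reduction |

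None of the six triggers is met. By comparison, Grade 3 vomiting or diarrhea for 5 days despite optimal management meets one, and 210 mg/m² is required.

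**Day count.** Let n be the days at Grade 3 or worse and k the days at Grade 4, so the days at Grade 3 are n − k. Two assumptions are made. All Grade 3 days are added together, which favors the protocol. Exactly 5 days counts as enough, following the bullet rather than the lead-in, which asks that the period be exceeded.

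- Current rule, read literally: n − k ≥ 5
- With *Grade 3 or higher* in the bullet: n ≥ 5
- With Grade 4 at any duration added: n − k ≥ 5 or k ≥ 1

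For n = 6, suppose Day 8 to Day 13 (13 − 8 + 1 = 6 days), at most Grade 2 on all other days, and Grade 1 by Day 22. For n = 4, the same pattern with two days fewer.

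| Episode | Days at Grade 3 (n − k) | Current rule | Grade 3 or higher | Grade 4 any duration added |
|---|---|---|---|---|
| n = 6, k = 0 | 6 | reduce | reduce | reduce |
| n = 6, k = 1 | 5 | reduce | reduce | reduce |
| n = 6, k = 2 to 6 | 4 to 0 | no trigger | reduce | reduce |
| n = 4, k = 0 | 4 | no trigger | no trigger | no trigger |
| n = 4, k = 1 to 4 | 3 to 0 | no trigger | no trigger | reduce |

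With n = 6 the current rule is inverted: more days at Grade 4 switch the trigger off. With n = 4 a Grade 4 episode escapes whether or not Grade 3 is taken to include Grade 4.

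**Size of the dose difference.** 267 − 210 = 57 mg/m², and 57 / 267 = 21.3%.

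**How often.** The documents give no rate for this situation.

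- Section 6.3.1.1 reports no Grade 3 or 4 vomiting in the two Phase II trials at 267 mg/m² (43 + 42 = 85 patients). Zero of 85 gives a one-sided 95% upper bound of 1 − 0.05^(1/85) = 3.5%, or about 0.035 × 250 ≈ 9 of the 250 patients planned for AEZS-108. This bounds any Grade 3 or 4 vomiting, not the gap itself, which is a subset.
- The related serious events listed in section 1.2.2 for the Phase II endometrial study include no vomiting or diarrhea.
- Against that, section 1.2.2 names vomiting and nausea, with leukopenia, as the most frequent serious drug reactions in the wider safety database, and diarrhea among the most frequent reactions overall. Serious is not the same as Grade 4.
- Grade-specific diarrhea rates are not given.

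**The case against.** **The wording.** A clinician could read Grade 3 as Grade 3 or higher, which removes the 6-day example. The separate febrile neutropenia lines do not settle the matter, because they carry different durations and had to be written separately. This stands as a limit on the 6-day example, which needs the literal reading. The 4-day example does not.

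**The choice of threshold.** Two other Grade 4 lines require 7 days, so a brief Grade 4 event does not always force a reduction, and mucosal inflammation, among the most frequent drug reactions, has no trigger at all. The list is a floor, not a full algorithm. That is fair, but the 7-day lines concern laboratory cytopenias. Febrile neutropenia, a clinical event described as life-threatening at Grade 4, is the closer model.

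**Clinical judgment.** The investigator may reduce the dose or withdraw the patient; 6.1.3 says "Any deviation from the planned dosing schedule must be commented on in the CRFs". Antiemetics started for symptoms continue as prophylaxis (6.3.1.1). Serious events are reported within 24 hours (7.2.1.4), and the DSMB receives safety analyses at intervals of no more than 6 months (section 4). All of this reduces the practical impact. None of it is a mandatory reduction.

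**The comparator.** Section 6.2.3 states no gastrointestinal trigger for doxorubicin and otherwise defers to the prescribing information, which is not in the documents. A new trigger for AEZS-108 alone would widen the difference in written rules between the arms. This is a fair cost to weigh. The arms already differ here, since the Grade 3 trigger exists only for AEZS-108.

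**Conclusion.** The concern holds, at minor severity. No text in the protocol or SAP makes a reduction mandatory after a short Grade 4 vomiting or diarrhea episode that has recovered to Grade 1, while 5 days of Grade 3 does require one. Re-dosing at 267 mg/m² is permitted, not required. Grade 4 episodes that also include 5 or more days at Grade 3 are already covered and are not part of this point.

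Confidence is high for the missing Grade 4 trigger, which survives either reading when fewer than 5 days in total are spent at Grade 3 or worse. The 6-day inversion rests on the literal reading. The situation is probably rare for vomiting; its frequency for diarrhea is unknown. The primary analysis, power and alpha are unaffected.

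**What to change.** Extend the gastrointestinal bullet in 6.1.3 with: *or Grade 4 vomiting or diarrhea of any duration*. This follows the list's own treatment of febrile neutropenia and closes both examples. At minimum, change Grade 3 to *Grade 3 or higher*; that closes the 6-day example but still leaves out Grade 4 episodes with fewer than 5 days at Grade 3 or worse.

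The edit is a few words. Because it concerns patient safety, section 10.3 requires approval by each ethics committee before implementation, so it is best bundled with the next amendment. The downsides are possibly a few more AEZS-108 dose reductions and a slightly larger difference from the written doxorubicin rules in 6.2.3.

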6.1.4 Emergency measures

A specific antidote in case of AEZS-108 overdose is not available. Close observation should be performed and adequate supportive care provided; adverse events/reactions should be treated symptomatically.

Adverse reactions that were observed under treatment with AEZS-108 at the proposed dosing schedule are summarized in the [Section 1.2.2](#).

6.2 Comparator drug – Doxorubicin

Commercially available doxorubicin products approved for use at the investigator's site will be used for the treatment of patients randomly allocated to Arm B. The trade name of the product used will be documented in the CRFs.

6.2.1 Description / general issues

Dry powder formulations, as well as ready-to-use solutions for intravenous use are allowed. The selection is at the discretion of the investigator, in line with applicable rules or regulations at study site.

All applicable instructions, warnings, and precautions in the prescribing information of the product used will be followed. References below to specific sections of the Prescribing Information should be verified with the prescribing information of the product actually used.

6.2.2 Reconstitution and administration

See corresponding Sections of the Prescribing Information.

6.2.3 Treatment modifications / delay of treatment

Dosage scheme:	60 mg/m ² by intravenous bolus injection, 1-hour intravenous infusion , or according to standard institution procedures, on Day 1 of 21-day (3-week) cycles Note: If the body weight is +/- 10% of the body weight measured at day 1 of the preceding cycle, the body weight measured at day 1 of the preceding cycle may be used for calculating the dose to be prepared in the pharmacy.
Dose adjustment:	(for starting dose)
- Renal function	at GFR below 10 ml/min.: 75 % of calculated dose
- Hepatic function	at serum bilirubin 1.2 to 3.0 mg/100 mL: 50 % of calculated dose; at serum bilirubin > 3.0 mg/100 mL: 25 % of calculated dose
Maximum duration / dose:	up to a cumulative lifetime dose of 550 mg/m ²
Treatment delay:	Subsequent cycles of study treatment should not begin before a patient has recovered to CTCAE Grade 1 from a drug-related adverse event (i.e., causality at least possibly related) that the investigator feels is clinically significant. No treatment delay is required for alopecia or anemia for which supportive therapy should be given according to study sites' clinical practice (see also 6.3.1.3). Re-treatment may be postponed for up to 2 weeks. A patient who has not recovered within 5 weeks after the last dose should be withdrawn and followed up as required. Note that some Prescribing Information cite the criteria used in study NSABP B-15, using a

doxorubicin/cyclophosphamide combination regimen: When necessary, the next cycle of treatment was delayed until the absolute neutrophil count was ≥ 1000 cells/mm³ and the platelet count was $\geq 100,000$ cells/mm³ and nonhematologic toxicities had resolved.

Dose reduction: (for retreatment)
75 % of the starting doses for neutropenic fever/infection.
Doxorubicin dosage must be reduced in case of hyperbilirubinemia as follows:

Plasma bilirubin concentration (mg/dL)	Dosage reduction (from starting dose)
1.2 - 3.0	50 %
3.1 - 5.0	75 %

For further information on treatment modifications, see Sections Dosage and Administration of the Prescribing Information.

